7.4.6 Pregnancy Test

A highly sensitive β subunit of Human chorionic gonadotropin (β -HCG) test in blood or urine will be performed in WOCBP for eligibility (see [Section 5.1](#)) and throughout the study as per SoE ([Table 1](#) or [Table 2](#)) and as needed.

When possible, for WOCBP patients treated with loncastuximab tesirine, a final pregnancy test should be performed ≥ 9 months post last drug dose, however, remote pregnancy test is acceptable.

Pregnancy test must be negative prior to study drug infusion.

If a urine pregnancy test is positive, the study treatment must be held pending pregnancy confirmation. If the pregnancy is confirmed by serum β -HCG test, study treatment will be discontinued permanently for the patient. Refer to [Section 8.5.2](#) for the handling of the patient and reporting the event.

[figure not shown]
7.4.7 Electrocardiograms

Three consecutive (also called triplicate) 12-lead electrocardiograms (ECGs) will be conducted at defined timepoints as per SoE ([Table 1](#) or [Table 2](#)) and [Table 6](#). The 12-lead ECGs will be performed after the patient is resting for at least 5 minutes.

At timepoints coinciding with blood sample collection, including PK, ECGs should be taken prior to blood collection, and, when applicable, before vital signs measurements. For loncastuximab tesirine arm a preferred sequence for triplicate ECG, vital signs, and PK sample assessments at End of Infusion (EOI) is demonstrated in [Figure 2](#).

ECGs will be submitted for a central review. Submission instructions for the central review will be provided in a separate manual. Assessments will include determination of heart rate and rhythm and the PR, QRS, QT, QTcF, and QTcB intervals. Eligibility and clinical decisions may be made based on the local ECG assessment.

Figure 2. Preferred Sequence for Triplicate Electrocardiogram (ECG), Vital Signs, and Pharmacokinetic (PK) Sample Assessments at End of Infusion (EOI)

7.5 Pharmacokinetics, Pharmacodynamics, and Immunogenicity

The PK, anti-drug antibody (ADA), and [REDACTED] will be collected as per SoE (Table 1). Additional biological samples may be collected by the Investigator when clinically indicated (e.g., at the time of significant AEs that are at least possibly related to the study drug) and may be used for PK, pharmacodynamics, [REDACTED].

When multiple samples are required at the same timepoint, collection of safety samples should be first, followed by PK, then ADA, [REDACTED].

In order to better understand the disease, metabolic disposition, and pharmacologic behavior of loncastuximab tesirine in humans, samples remaining after primary analyses may be utilized for further analysis.

Biological samples may be retained for up to 10 years to further address scientific questions as new information in regard to the disease or the study drug becomes available.

For detailed instructions related to central laboratory sample collection, labeling, processing, storage, or shipment refer to the appropriate laboratory manual(s).

7.5.1 Pharmacokinetics

The concentration in serum of loncastuximab tesirine (total antibody), PBD-conjugated antibody, and unconjugated warhead SG3199 for samples taken prior to and immediately after dosing on Cycles 1 through 6, and end of treatment in patients on loncastuximab tesirine will be assessed by a central laboratory designated by the Sponsor using validated bioanalytical methods. In addition, matching PK samples will be drawn at ADA collection time points from Cycle 7 and beyond during study treatment.

Approximately 6 mL of whole blood will be collected as per [Table 1](#) and [Table 6](#). Blood should be drawn from a vein away from the one used for study drug infusion.

PK samples must be stored at $\leq -70^{\circ}\text{C}$. Please refer to the laboratory manual for detailed instructions regarding specimen handling and shipment.

At timepoints coinciding with ECG collection, PK blood collection should occur immediately after the end of the ECG recording and, when applicable, after vital signs.

To understand the metabolic disposition of loncastuximab tesirine in humans, samples remaining after PK analysis is complete may be pooled among patients for potential metabolite identification.

Table 6. Sampling Schedule for ECG, PK, ADA and [REDACTED]

Cycle	Day	ECG timepoint	PK timepoint loncastuximab tesirine arm only	ADA timepoint loncastuximab tesirine arm only	[REDACTED]
Screening	-28 to -1	X			
C1-C6	D1	C1: Pre-dose only C2: Pre-dose for all subjects & EOI (Within 10 min prior to EOI) for loncastuximab tesirine arm only	X Pre-dose & EOI: Within 10 min post EOI	C1, C3, and C5 only: Pre-dose	
C7 & Beyond	D1		C7, then every other cycle Pre-dose	C7, then every other cycle Pre-dose	
EOT		Anytime during EOT visit	X	X	
Follow-Up				If ADA positive is detected, additional ADA samples may be requested for testing every 12 weeks until the ADA titer falls to the baseline level	

**Pre-dose: preferably within 2 h prior to start of infusion

Abbreviations: ADA=anti-drug antibody; C=cycle; D=day; ECG=electrocardiogram; EOI=end of infusion; EOT=end-of-treatment; h=hour; min=minute; PK=pharmacokinetics; [REDACTED]; IP=Investigational Product

7.5.2 Immunogenicity

Detection of ADAs will be performed by using a screening assay for identification of antibody-positive samples/patients, a confirmation assay, and titer assessment and will be performed using the Meso-Scale Discovery Electrochemiluminescence platform. If an ADA is confirmed, a functional assay for the assessment of the neutralizing capacity of the ADA will be performed.

Blood samples for ADA testing will be collected pre-dose on C1D1, then Day 1 of every other cycles from patients assigned to loncastuximab tesirine arm only. Up to 6 mL of whole blood will be collected each time as per [Table 1](#) and [Table 6](#).

Blood should be drawn from a vein away from the one used for study drug infusion.

For patients who test positive for ADA, additional ADA samples may be requested for testing every 12 weeks following the EOT visit until the ADA titer falls to the baseline level

ADA samples must be stored at $\leq -70^{\circ}\text{C}$. Please refer to the laboratory manual for detailed instructions regarding specimen handling and shipment.

7.6 Patient Reported Outcomes

The impact of study treatment on disease- related symptoms, symptomatic adverse events, as well as various aspects of patient's health-related quality of life (HRQoL), will be assessed by:

- EuroQoL-5 Dimensions-5 Levels (EQ-5D-5L) ([Appendix 4](#)).
- Functional Assessment of Cancer Therapy – Lymphoma (FACT-Lym) ([Appendix 5](#)).

- GP5 item of FACT-Lym ([Appendix 6](#))
- Selected symptomatic adverse events from the PRO-CTCAE library, including fatigue, swelling, rash, nausea, diarrhea, abdominal pain, and cough ([Appendix 7](#)).

Questionnaires will be completed in the respondent's native language, at the scheduled time points as per [Table 1](#) or [Table 2](#). Responses to PRO questionnaires will be collected electronically.

1. Both EQ-5D-5L and FACT-Lym will be completed at study site with the exception of EQ-5D-5L follow -up assessments, which may be completed by phone (see [Table 1](#) or [Table 2](#)).
2. Both GP5 item of FACT-Lym and selected PRO-CTCAE items will be completed by patients at home, with the exception of the PRO-CTCAE items at baseline (Cycle 1 Day1), which will be answered at study site (see [Table 1](#) or [Table 2](#)).

Questionnaires should always be administered prior to clinical assessment if applicable. The patient should be given instructions, space, time, and privacy to complete the questionnaires by themselves and without any assistance from anyone else. The study coordinator should encourage the patient to complete the questionnaires without any missing responses.

7.6.1 EuroQol-5 Dimensions-5 Levels (EQ-5D-5L)

EQ-5D-5L is a standardized, generic instrument for describing health status as the patient experiences them “today.” It is used for clinical and economic evaluation ([EuroQol Research Foundation, 2019](#)). The EQ-5D-5L consists of two parts:

- The descriptive system: consists of five single-item dimensions: mobility, self-care, usual activities, pain/discomfort, and anxiety/depression. Each dimension comprises five levels of perceived problems (e.g., none, slight, moderate, severe, extreme/unable to).
- The visual analog scale (VAS): patients are asked to rate their current health on a 100-point scale, ranging from ‘the best health you can imagine’ (score 100) and ‘the worst health you can imagine’ (score 0). Patients are asked to mark an “X” on the VAS to indicate their own health and then to report the score in a text box. If there is a discrepancy between where the patient has placed the X and the number, he/she has written in the box, the number in the box is to be entered in the CRF together with a comment indicating the discrepancy. Patients will complete this questionnaire as per the SoE ([Table 1](#) or [Table 2](#)).

7.6.2 Functional Assessment of Cancer Therapy - Lymphoma (FACT-Lym)

FACT-Lym (Version 4) is a HRQoL questionnaire validated in patients with B-cell and other types of NHL ([Cella et al., 2005](#); [Hlubocky et al., 2013](#)). It has been widely used in NHL trials, for example, the phase III GADOLIN study in patients with rituximab-refractory indolent NHL including FL ([Cheson et al., 2017](#)), the phase III GALLIUM study in previously untreated, advanced indolent NHL including FL ([Thielen et al., 2019](#)), and the RESORT E4402 study in patients with low–tumor burden NHL including FL ([Wagner et al., 2015](#)). FACT-Lym consists

of a general HRQoL assessment (FACT-G) and a disease-specific subscale (Lymphoma subscale, LymS). FACT-G (27 items) measures four functional dimensions: physical well-being (PWB), social/family well-being (SWB), emotional well-being (EWB), and functional well-being (FWB). The LymS (15 items) addresses symptoms and functional limitations that are important to patients with NHL, such as pain, lump or swelling, fatigue, fever, night sweats, itching, and weight loss. All items use a 0-4 ordinal measurement where 0 = not at all, 1 = a little bit, 2 = somewhat, 3 = quite a bit, and 4 = very much. The summary scores for PWB, SWB, EWB, FWB and LymS are computed as the sum of corresponding items (after reversed coding for the negatively stated items) with higher values indicating better quality of life. Three composite scores are also derived: Trial Outcome Index (TOI: sum of PWB, FWB, LymS), FACT-G total (sum of PWB, SWB, EWB, FWB), and FACT-Lym total (sum of FACT-G total and LymS). Patients will complete this questionnaire as per the SoE ([Table 1](#) or [Table 2](#)).

7.6.3 FACT-Lym GP5

A single item from the FACT-Lym, GP5, will be administered to assess the extent of perceived bother due to symptomatic AEs. Evidence exists for the validity of this item and its usefulness as an overall summary measure of burden due to symptomatic treatment toxicities ([Pearman, 2018](#)). Patients will complete this question as per the SoE ([Table 1](#) and [Table 2](#)).

7.6.4 Patient-Reported Outcomes version of the Common Terminology Criteria for Adverse Events (PRO-CTCAE™) – Selected Items

PRO-CTCAE is a patient-reported outcome measurement system developed to evaluate symptomatic toxicity in patients on cancer clinical trials. The PRO-CTCAE Item Library contains 124 items representing 78 symptomatic toxicities drawn from the Common Terminology Criteria for Adverse Events (CTCAE). PRO-CTCAE items assess the symptom attributes of frequency, severity, interference, amount, presence/absence. Each symptomatic AE is evaluated by 1-3 attributes. The PRO-CTCAE has been developed as a standardized measurement that can provide a flexible fit-for-purpose approach to assess relevant symptomatic AEs for the trial ([Kluetz 2016](#)). The PRO-CTCAE Measurement System are validated in accordance with well-established PRO instruments ([Dueck 2015](#)). The PRO-CTCAE items included in this study are fatigue, swelling, rash, nausea, diarrhea, abdominal pain, and cough. These AEs are selected in an unbiased manner based on the symptomatic adverse events reported in Loncastuximab tesirine 402-201 trial of patients with R/R DLBCL ([Carmelo Carlo-Stella, EHA 2020](#)) and Idelalisib package insert for FL indication. Specifically, symptomatic AEs with occurrence in at least 20% of patients treated with either therapy are selected. Patients will complete these questions as per the SoE ([Table 1](#) or [Table 2](#)).

8 Adverse Events

Reporting of AEs to competent authorities and Independent Review Boards (IRBs)/Independent Ethics Committees (IECs) will be consistent with current laws, regulations, and guidelines.

8.1 Definition of Adverse Events and Serious Adverse Events

8.1.1 Adverse Events

An AE is defined as any untoward medical occurrence in a patient or clinical investigation subject administered a pharmaceutical product, which does not necessarily have to have a causal relationship with this treatment.

An AE does not include the following:

- Medical or surgical procedures such as surgery, endoscopy, tooth extraction, and transfusion. The condition that led to the procedure may be an adverse event and must be reported.
- Pre-existing diseases, conditions, or laboratory abnormalities present or detected before the screening visit that do not worsen.
- Situations where an untoward medical occurrence has not occurred (e.g., hospitalization for elective surgery, social and/or convenience admissions)

Test results collected during the study (e.g., laboratory values, physical examination, ECGs, etc.) or identified from review of other documents may constitute AEs if deemed clinically significant.

8.1.2 Serious Adverse Events

A SAE is defined as any AE that:

- results in death.
- is life threatening.
- requires inpatient hospitalization or prolongation of existing hospitalization (hospitalization for elective procedures or for protocol compliance is not considered an SAE).
- results in persistent or significant disability/incapacity.
- is a congenital anomaly/birth defect.
- an important medical event that does not meet the preceding criteria but based on appropriate medical judgment may jeopardize the patient or may require medical or surgical intervention to prevent any of the outcomes listed above.

8.1.3 Clinical Laboratory Abnormalities and Other Abnormal Assessments as Adverse Events or Serious Adverse Events

Laboratory abnormalities (e.g., clinical chemistry, hematology, and urinalysis) or other abnormal assessments (e.g., electrocardiogram, x-rays, vital signs) without clinical significance are not recorded as AEs or SAEs. However, laboratory abnormalities/other abnormal assessments that require medical or surgical intervention or lead to pharmaceutical product interruption, modification, or discontinuation must be recorded as an AE, as well as an SAE, if applicable. If the laboratory abnormality/other abnormal assessment is consistent with a clinical diagnosis, report the adverse event using the diagnosis (i.e., anemia), not the laboratory result (i.e., decreased hemoglobin).

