Abbreviations: ADA: anti-drug antibody; AE: adverse events; BP: blood pressure; β -HCG: β subunit of Human chorionic gonadotropin; C: cycle; C1D1: cycle 1 day 1; [REDACTED] CMV: cytomegalovirus; CT: computerized tomography; ECG: electrocardiogram; ECOG: Eastern Cooperative Oncology Group; EOI: end of infusion; EOT: end of treatment; FACT-Lym: The Functional Assessment of Cancer Treatment-Lymphoma questionnaire; FDG: (18)F-fluorodeoxyglucose; [REDACTED]; HBV: hepatitis B virus; HCV: hepatitis C virus; HIV: human immunodeficiency virus; HR: heart rate; ICF: informed consent form; IV: Intravenous; MRI: Magnetic resonance imaging; PCR: polymerase chain reaction; PK: pharmacokinetics; PRO-CTCAE: Patient-Reported Outcomes Version of the Common Terminology Criteria for Adverse Events; RR: respiratory rate; SAE: serious AEs; Temp: temperature;.

Visit Scheduling Windows:

- Treatment Period: Visit day \pm 3 days (excluding C1D1 which is the reference day).
- EOT: As soon as possible after decision to discontinue the study treatment but preferably at least 30 days after last dose of study treatment unless a new anticancer treatment is planned to be administered before the 30 days, in which case EOT should be conducted before initiation of the new anticancer treatment.
- Follow-up Period: Visit day \pm 14 days.

²Vitals should be taken at pre-dose and EOI for every loncastuximab tesirine dosing visit.

³Positron-emission tomography-computed tomography will be used to perform imaging study. If disease is not FDG-avid at baseline, CT or MRI may be used. Screening imaging must be performed within 4 weeks prior to C1D1 and the same assessment method must be used throughout the study. Week 6 and Week 12 imaging should be performed within \pm 5 days of the scheduled timepoint. All other imaging for disease assessment should be performed within \pm 2 weeks of the

scheduled time point. Imaging for disease assessment should be performed at the scheduled timepoint even if drug dosing is delayed. Additional disease assessments may be obtained, if clinically indicated.

⁴During follow-up period disease assessments to be performed in patients who discontinued study treatment for reasons other than disease progression or initiation of other anti-cancer therapy (except for hematopoietic stem cell transplant).

⁵ \leq 3days prior to administration of study treatment for loncastuximab tesirine arm patients.

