6.7 Dose Delays and Modifications

6.7.1 Dose Delays and Modifications for Loncastuximab Tesirine and Idelalisib

The criteria and guidance for dose delay and dose modifications of loncastuximab tesirine and idelalisib are summarized in [Table 4](#) and [Table 5](#), respectively.

Table 4. Criteria for Dose Delay or Dose Modification of Loncastuximab Tesirine

Toxicity	Loncastuximab Tesirine
Grade ≥ 3 non-hematologic adverse events	
Hold until the toxicity resolves to Grade ≤ 1, (Grade 1 or baseline for peripheral neuropathy)If dosing is delayed by more than 3 weeks and the toxicity is considered at least possibly related to loncastuximab tesirine, then subsequent doses must be reduced by 50%. If the toxicity recurs, subsequent doses must be reduced by an additional 50%A maximum of 2 dose reductions are allowedNote: Patients who have a toxicity meeting the criteria for dose reduction following Cycle 2 will receive the protocol-specified dose of 75 $\mu\text{g}/\text{kg}$ for Cycle 3, i.e., they will not have an additional dose reduction for Cycle 3
Grade ≥ 2 edema, effusion	
Hold until the toxicity resolves to Grade ≤ 1If dosing is delayed by more than 3 weeks and the toxicity is considered at least possibly related to loncastuximab tesirine, then subsequent doses must be reduced by 50%. If the toxicity recurs, subsequent doses must be reduced by an additional 50%A maximum of 2 dose reductions are allowedNote: Patients who have a toxicity meeting the criteria for dose reduction following Cycle 2 will receive the protocol-specified dose of 75 $\mu\text{g}/\text{kg}$ for Cycle 3, i.e., they will not have an additional dose reduction for Cycle 3

Toxicity	Loncastuximab Tesirine
Grade ≥ 3 neutropenia or thrombocytopenia	
• Hold until toxicity resolves to Grade ≤ 2• If dosing is delayed by more than 3 weeks and the toxicity is considered at least possibly related to loncastuximab tesirine, then subsequent doses must be reduced by 50%. If the toxicity recurs, subsequent doses must be reduced by an additional 50%• A maximum of 2 dose reductions are allowed• Note: Patients who have a toxicity meeting the criteria for dose reduction following Cycle 2 will receive the protocol-specified dose of 75 $\mu\text{g}/\text{kg}$ for Cycle 3, i.e., they will not have an additional dose reduction for Cycle 3

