Grade 4 infusion related reaction	
• Permanently discontinue loncastuximab tesirine
Hy's law (AST and/or ALT $> 3 \times \text{ULN}$ and bilirubin $> 2 \times \text{ULN}$)	
• Permanently discontinue loncastuximab tesirine. Hy's law defined as: AST and/or ALT $> 3 \times \text{ULN}$ and bilirubin $> 2 \times \text{ULN}$, and without initial findings of cholestasis (ALP activity $< 2 \times \text{ULN}$) and no other reason that could explain the combination of increased transaminases and serum total bilirubin, such as viral hepatitis A, B, or C, preexisting or acute liver disease, or another drug capable of causing the observed injury

Table 5. Criteria for Dose Delay or Dose Modification of Idelalisib

Toxicity	Idelalisib
Grade ≥ 2 symptomatic pneumonitis of any severity	Permanently discontinue idelalisib
Grade 2 increased ALT/AST/bilirubin or diarrhea	Maintain idelalisib dose. Monitor at least weekly until normal
Grade 3 increased ALT/AST/bilirubin or diarrhea	Withhold idelalisib. Monitor at least weekly until normal, then may resume idelalisib at 100 mg BID.
Grade 4 increased ALT/AST/bilirubin or diarrhea	Discontinue idelalisib permanently
Grade 3 neutropenia and/or thrombocytopenia	Maintain Idelalisib dose. Monitor ANC and/or platelet count at least weekly
Grade 4 neutropenia and/or thrombocytopenia	Withhold idelalisib. Monitor ANC and/or platelet count at least weekly. When neutropenia and thrombocytopenia are Grade 3 or less, may resume idelalisib at 100 mg BID
Grade ≥ 3 sepsis or pneumonia	Withhold idelalisib until infection has resolved.
Active CMV infection of any grade or viremia (positive PCR or antigen test)	Withhold idelalisib until the infection and viremia have resolved. If idelalisib is resumed, monitor by PCR or antigen for CMV reactivation at least monthly.
Suspected PJP infection of any grade.	Withhold idelalisib. Permanently discontinue idelalisib if PJP infection is confirmed.
Other Grade ≥ 3 non-hematologic toxicities	Withhold idelalisib until resolved, then may resume idelalisib at 100 mg BID. If the same grade ≥ 3 toxicity recurs after resuming idelalisib, permanently discontinue idelalisib
Anaphylaxis, Intestinal Perforation, Stevens-Johnson syndrome (SJS) and toxic epidermal necrolysis (TEN)	Permanently discontinue idelalisib

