9.8.1 Adverse Events

The focus of AE summarization will be on TEAEs. A TEAE is defined as an AE that occurs or worsens in the period extending from the first dose of study treatment until 30 days after the last dose of study treatment or start of new anti-cancer therapy, whichever is earlier.

All TEAEs will be summarized. Summary tables will be presented to show the number of patients reporting TEAEs by severity grade and corresponding percentages. A patient who reports multiple TEAEs within the same Preferred Term (or System Organ Class) is counted only once for that Preferred Term (or System Organ Class) using the worst severity grade.

Separate summaries will be prepared for TEAEs classified as severe or life-threatening (\geq Grade 3); study treatment-related AEs; AEs leading to treatment interruption, modification, or discontinuation; SAEs; and death.

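### Recording of Grade 3 neutropenia or thrombocytopenia as an AE follows different rules in the two arms, because Section 8.1.3 ties mandatory recording to dosing action

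*Combined protocol and SAP*

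**What the plan says.** Section 8.1.3 sets one recording rule for both arms. Laboratory abnormalities "without clinical significance are not recorded as AEs or SAEs". Those that need medical or surgical intervention, or that "lead to pharmaceutical product interruption, modification, or discontinuation must be recorded as an AE", have to be entered. Section 8.1.1 leaves the remainder to judgement: test results "may constitute AEs if deemed clinically significant", with no grade threshold.

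The dosing tables in Section 6.7.1 treat the same count differently:

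- Table 4, loncastuximab tesirine, Grade 3 or higher neutropenia or thrombocytopenia: "Hold until toxicity resolves to Grade" 2 or lower.
- Table 5, idelalisib, Grade 3: "Maintain Idelalisib dose. Monitor ANC and/or platelet count at least weekly".
- Table 5, idelalisib, Grade 4: "Withhold idelalisib. Monitor ANC and/or platelet count at least weekly".

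Table 1 times loncastuximab tesirine hematology at no more than 3 days "prior to administration of study treatment for loncastuximab tesirine arm patients", so a scheduled Grade 3 result arrives at the dosing decision.

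On analysis, Section 9.8.1 states that "The focus of AE summarization will be on TEAEs" and plans a separate summary of Grade 3 or higher TEAEs. Section 9.8.2 separately summarizes laboratory shifts by CTCAE grade and worst-case post-baseline results.

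**The concern.** A rule with identical wording for both arms operates differently once it is linked to dosing action, because the dosing tables differ at Grade 3. The same laboratory value then passes through a mandatory route in one arm and a judgement in the other, made by site staff who know the treatment.

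Cytopenias are leading toxicities of both drugs. Section 1.2.3 quotes Grade 3 or higher neutropenia of 27% on idelalisib. For loncastuximab tesirine it quotes 16.9% neutropenia, 14.8% neutrophil count decreased and 12.0% thrombocytopenia. AE incidence and severity is a secondary endpoint, and Sections 2.1 and 9.1 say that the sample size was driven by the need for safety data. At stake is whether the two arms' Grade 3 or higher cytopenia TEAE rates, set side by side, measure the same thing.

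**Working it through.** The plan gives no figure to reproduce. The check applies the Section 8.1.3 triggers to the hematology rows of Tables 4 and 5, then asks how many patients the difference could touch.

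**1. Rule by grade, no other intervention needed**

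| Count | Loncastuximab tesirine | Idelalisib |
|---|---|---|
| Grade 3, present at dosing | Held, so mandatory AE | Continued, so AE only if judged clinically significant |
| Grade 3, recovered before next dose | No hold, so judgement | Continued, so judgement |
| Grade 4, present when a dose is due | Held, so mandatory AE | Withheld, so mandatory AE |

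The asymmetry is confined to the first row. A Grade 3 count that does need intervention is mandatory in both arms.

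**2. Idelalisib patients exposed to discretion**

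Inputs: 27% Grade 3 or higher neutropenia (Section 1.2.3; 125 adults with indolent lymphoma); 150 patients randomized 2:1 (Section 9.1), so 150 × 1/3 = 50 on idelalisib; share of those events peaking at Grade 3 taken as 40-70% (assumption, not in the documents).

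- 27% × 0.40 = 10.8 points; × 50 = 5.4 patients.
- 27% × 0.70 = 18.9 points; × 50 = 9.45 patients.

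That is about 5-9 patients whose recording is discretionary. It is not a count of missed events.

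**3. From exposure to bias**

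Suppose the true Grade 3 rate p is equal in both arms, every case is recorded on loncastuximab tesirine, and a share r is recorded on idelalisib. The spurious difference is p × (1 − r). All values here are assumptions:

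- p = 10%, r = 50%: 5 points.
- p = 30%, r = 50%: 15 points.
- any p, r = 100%: 0 points.

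The range is 0-15 points, with more events shown on loncastuximab tesirine.

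**4. Why the sign is not fixed**

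Step 3 assumes complete detection and recording on loncastuximab tesirine. Let d be the chance that an episode is measured at all, and q the share of measured episodes recorded on loncastuximab tesirine. The difference becomes p × (d_L × q − d_I × r), which is negative whenever d_I × r exceeds d_L × q.

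Scheduled hematology in the first 28 weeks (7 cycles × 4 weeks on idelalisib):

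- Idelalisib (Table 2), Days 1 and 15 of cycles 1 to 7: 7 × 2 = 14 samples.
- Loncastuximab tesirine (Table 1), Day 1 every 3 weeks, at weeks 0, 3, …, 27: 10 samples.

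Table 5 also adds at least weekly counts once Grade 3 appears on idelalisib. From cycle 8 the scheduled order reverses (every 4 weeks against every 3). The documents give none of d, q or r.

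**The case against.** The strongest case against has four parts.

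*Grade 3 would be recorded anyway.* Section 8.2 has clinically significant conditions that start or worsen after consent reported as AEs in both arms, and Table 5 requires at least weekly counts at Grade 3, so such a value is hard to call insignificant. This has weight and is why the number missed could be zero. But Section 8.2 still turns on clinical significance, Section 8.1.3 links compulsory entry to intervention or drug action rather than to grade, and a repeat count is not clearly an intervention.

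*Sampling pushes the other way.* This stands. Denser early sampling on idelalisib, together with loncastuximab tesirine counts that recover before dosing, can offset or reverse the effect.

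*The laboratory tables already cover it.* Partly. The shift and worst-case summaries of Section 9.8.2 do not depend on AE entry. They do not alter the TEAE tables, however, and Section 9.8 does not name them as the basis for comparing cytopenias between arms.

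*Consequence is low.* The safety objective concerns loncastuximab tesirine and is not worded as a comparison, the analysis is descriptive, and the Section 4.3 stopping rules do not single out cytopenias. This limits the weight of the point. It does not make the two columns comparable.

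A reader might go further and infer that the main safety table is tilted against loncastuximab tesirine, or that 11-19 percentage points of idelalisib neutropenia will be lost. The documents support neither. The first ignores sampling; the second mistakes a pool exposed to judgement, itself built on an assumed Grade 3 share, for an estimate of bias.

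**Conclusion.** The point holds as a difference in recording rules, not as a demonstrated bias of known sign. For a Grade 3 neutrophil or platelet count with no other intervention, entry as an AE is compulsory when loncastuximab tesirine is held and a matter of site judgement when idelalisib continues. At Grade 4 the dosing-interruption trigger applies in both arms.

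The rule on its own favours fuller recording on loncastuximab tesirine. The net direction and size cannot be determined from the documents. The 5-9 of 50 idelalisib patients exposed to discretion depends wholly on the assumed 40-70% Grade 3 share of the quoted 27%, and that 27% covers neutropenia only, in a wider indolent lymphoma group. Efficacy is unaffected. The change is worth making because it is cheap and takes a rule-driven difference out of the Grade 3 or higher TEAE table.

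**What to change.** Two changes:

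1. In Section 8.1.3, with matching eCRF guidance, require each episode of Grade 3 or higher neutropenia or thrombocytopenia to be recorded as one AE in both arms, under its diagnosis term, whatever action is taken with study drug. Counting episodes rather than values avoids repeat entries during weekly monitoring and fits the section's existing preference for diagnoses over laboratory results.
2. In Section 9.8, base the between-arm cytopenia comparison on worst post-baseline CTCAE laboratory grade from the hematology data already collected, including patients already treated, and state the two sampling schedules beside it.

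The cost is a short addition to each section, the eCRF guidance and some extra AE entries, mainly on idelalisib. Differences in sampling remain and have to be disclosed. No change to Table 4 or Table 5 is implied.
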